#### References:

iv. Clinical examination including joint examination, anthropometry and vital signs (See also Appendix I)

A musculoskeletal comprehensive examination to obtain counts of swollen and tender joints will take place in every visit. In addition as shown in appendix I other evaluations including seated blood pressure, waist circumference and height and weight will be obtained.

v. DEXA scan

A whole body DEXA scan will be performed on the 50 RA patients who will be randomized to escalation of treatment. As shown in appendix I it will be performed at the time of Study Visit I and II. The purpose will be to evaluate the amount and the pattern of adipose tissue distribution in the body which is an important parameter and risk factor for atheromatous and cardiovascular disease. Radiation exposure is minimal (0.001 rem) per study per patient and there are no risks associated with this study. Pregnancy test as noted earlier will be performed prior to DEXA for every female participant with child bearing potential.

vi. Questionnaire completion (See also Appendix III)

Patients will be asked to complete questionnaires at the time of their study visits as indicated in Appendix III. The questionnaires will be administered in English and Spanish and with the assistance of a research coordinator. The questionnaire list is included below

SF36  
HAQ  
Health and life questionnaire  
Physical activity questionnaire

Medical history  
 Prednisone history  
 RA history  
 Oral Health  
 Medication history  
 RA medication history  
 Joint Count  
 Personal history  
 RA LTRC respiratory symptoms  
 RA LTRC Occupational and environmental exposures  
 400m Walk Test

#### 4. STUDY DRUGS OR DEVICES

The drugs that will be prescribed to subjects in this study, listed below, are FDA approved for the indicated use, at the prescribed dose(s), and in the patient populations being studied.

##### TNF INHIBITORS

ENBREL® (etanercept)  
 REMICADE® (infliximab)  
 SIMPONI® (golimumab)  
 HUMIRA® (adalimumab)  
 CIMZIA ( certolizumab)

##### OTHER RA MEDICATIONS

PLAQUENIL® (Hydroxychloroquine sulfate)  
 ARAVA® (leflunomide)  
 Methotrexate  
 Sulfasalazine  
 Folic Acid  
 Prednisone

[figure not shown]
#### 5. STUDY INSTRUMENTS

SF 36 (Appendix IV): The SF 36 questionnaire is the most widely used tool for measuring patient-reported quality of life. It captures practical, reliable, and valid information about functional health and well-being from the patient's point of view. This surveys is for adults 18 years of age and older, and can be self-administered or interview-administered. Is extensively validated and standardized.

HAQ (Appendix V): The Health Assessment Questionnaire (HAQ) was developed originally in 1978 by [name], and colleagues at Stanford University. It was designed to represent a model of patient-oriented outcome assessment. The HAQ has been administered and validated in patients with a wide variety of rheumatic diseases, including rheumatoid arthritis.

It is one of the first self-report functional status (disability) measures, and is widely used throughout the world. Although it measures functional status it was found to be the best predictor of mortality in patients with RA. The HAQ has become a de facto mandated outcome measure for clinical trials in rheumatoid arthritis and some other diseases. Is extensively validated and standardized.

Health and life questionnaire (Appendix VI): This questionnaire includes several instruments designed to measure psychosocial characteristics that may be important in understanding the causes of cardiovascular disease. These psychosocial factors may themselves lead to increased risk of cardiovascular disease or may interact with other traditional risk factors, such as diet or sedentary lifestyle. The areas assessed as part of this questionnaire include neighborhood, characteristics, depression, stress, and social support. This is a self-administered form. The terms used in the questionnaire should require no explanation, because they are used in the way they tend to be used by most

people in everyday life. This questionnaire has been extensively used in research before and also during the Multi-Ethnic Study of Atherosclerosis (MESA).

Physical activity questionnaire (Appendix VII): The International Physical Activity Questionnaires (IPAQ) is a standardized questionnaire that will be used to evaluate levels of physical activity. It can be used for either telephone or self-administered methods are available. The purpose of the questionnaires is to provide common instruments that can be used to obtain internationally comparable data on health related physical activity. The development of an international measure for physical activity commenced in Geneva in 1998 and was followed by extensive reliability and validity testing undertaken across 12 countries (14 sites) during 2000. The final results suggest that these measures have acceptable measurement properties for use in many settings and in different languages, and are suitable for national population-based prevalence studies of participation in physical activity.

Medical history, Prednisone history, RA history, Medication history (Appendices VIII, IX, X, XI): these questionnaires only collect history information from the patient, do not require a scoring system and do not need to be standardized or validated as they are used only as history taking tools. However they have been used in our previously federally funded study (ESCAPE I) in the context of MESA (Multi-Ethnic Study of Atherosclerosis)

Oral Health Assessment (Appendix XII): this questionnaire collects information about oral conditions, dental and periodontal disease. RA can affect the oral cavity causing xerostomia (dry mouth) which may predispose to dental disease. In addition a theory linking RA pathogenesis with periodontal disease is under investigation by the research community. This questionnaire does not provide an "oral health score" and is not a standardized data collection tool. It is a symptom and personal history collection form.

RA medication (Appendix XIII) and Joint count (Appendix XIV) questionnaires: these questionnaires only collect history information from the patient, do not require a scoring system and do not need to be standardized or validated as they are used only as history taking tools. Appendix XIII collects information on medications for the treatment of rheumatoid arthritis (not other medications). Appendix XIV collects information about the number of joints that are affected by RA since numbers of affected joints inform therapeutic decisions.

Personal history (Appendix XV): The Personal History questionnaire is used to collect information on socio-economic status (SES) and smoking and drinking habits, all of which are related to an individuals risk of cardiovascular disease. It has been used in previous studies such as in ESCAPE I and in the Multi-Ethnic study of atherosclerosis (MESA)

[figure not shown]
Lung Tissue Research Consortium (LTRC) respiratory symptom questionnaire (Appendix XVI) and LTRC occupational and environmental exposure (Appendix XVII): Respiratory involvement is the second cause of mortality in patients with RA and symptoms overlap with those from cardiovascular disease. We will use these questionnaires to investigate the risks for respiratory involvement and the prevalence of respiratory symptoms in our research subjects. This questionnaires are used extensively in pulmonary disease related research by entities such as the Lung Tissue Research Consortium (LTRC) and the American Thoracic Society.

400m Walk Test (Appendix XVIII): Participants will be asked to walk a short distance (400m). This will happen under supervision by the research coordinator and after cardiovascular contraindications have been ruled out by the attached questionnaire. Vital signs will be recorded prior to and after the completion of the test. All information will be recorded in the attached questionnaire. The purpose of this test is to evaluate the tolerance to mild exercise and the response of the cardiovascular system (Heart Rate and Blood pressure) to brisk walking. This test has been used in several studies including MESA.

## 6. STUDY SUBJECTS

(this section includes references)

Subjects fulfilling the 2010 ACR-EULAR diagnostic criteria for RA (1) but without any history of previous self reported or physician diagnosed cardiovascular events will be eligible for participation in the study. The goal is to

enroll 150 patients for the purposes of this protocol. Subjects will be recruited from the arthritis clinics at the Columbia University.

Among the subjects above, patients with RA who have moderate to high disease activity as defined by a CDAI higher than 10 will be given the opportunity to consent for randomization in treatment with either a TNF inhibitor or alternative treatment and return for follow up visits as indicated in earlier sections. 50 patients will be randomized to this aspect of the study.

15 subjects without RA and without prior cardiovascular disease will also be recruited. These subjects will be recruited among patients in the internal medicine clinics at the Columbia University or from friends of the recruited patients.

#### Inclusion Criteria

For patient participation in Study Visit I (150 participants):

Diagnosis of RA

Age > 18 years old

For patient participation in the randomized treatment and subsequent visits (50 of the initially recruited 150 participants):

Moderate to high RA disease activity defined by a CDAI of > 10

Stable dose of Methotrexate for 6 weeks prior to enrollment;

Stable doses of NSAID and prednisone (if already taking these medications) for 2 weeks prior to study

For control participation (15 controls):

Age > 18 years old

Absence of diagnosis of RA.

#### Major Exclusion Criteria

For patient participation in Visit I (150 participants):

Prior self-reported physician diagnosed CV event (MI; angina; stroke or TIA; HF; prior CV procedure (e.g., coronary artery bypass graft, angioplasty, valve replacement, pacemaker);

Contraindications to having a PET-CT scan or receive adenosine or FDG.

Active treatment for Cancer

For patient participation in the randomized treatment and follow up visits (50 of the 150 initially enrolled participants):

Uncontrolled hypertension

Diabetes

Smoking

Treatment with a TNF inhibitor or other biologic currently or within the last 6 months

Treatment with any non-biologic DMARD other than MTX in the past two months;

Untreated positive PPD or active tuberculosis

History of Lymphoma and Melanoma

Ejection Fraction (EF) < 40% (if not known in advance then the Study Visit I Echocardiogram results will be used to exclude the patient in this part of the study)

Change with NSAID/Prednisone dosage in last 2 weeks

Participation in other research studies involving imaging/radiation exposure

A copy of the Patient Screening Form is attached to the protocol as Appendix XXV.

For controls :

Prior self-reported or physician diagnosed CV event (MI; angina; stroke or TIA; HF; prior CV procedure (e.g., coronary artery bypass graft, angioplasty, valve replacement, pacemaker);  
 Contraindications to having a PET-CT scan or receive adenosine or FDG.  
 Uncontrolled hypertension.  
 Participation in other research studies involving imaging/radiation exposure

A copy of the Control Screening Form is attached to the protocol as Appendix XXVI and a copy of the Radiation Screening Form is attached as Appendix XXVII.

RA subjects and controls who do not consent to any aspect of the study such as to the blood draws or to evaluation with PET-CT will be excluded from this study.

In addition patient and controls who are receiving treatment for cancer, with cognitive inability will be excluded from the study.

Patients and controls on statin treatment for hyperlipidemia should ideally stay on a stable dose and the same statin agent for the duration of the study. We will encourage but not require the participants and their treating physicians to do so. The reason is that statins are known to have an anti-inflammatory effect and may interfere with analysis/interpretation of the amount of myocardial inflammation as measured during PET-CT imaging. Recognizing however, that some patients will be newly diagnosed with hypercholesterolemia during the clinical trial portion of the study and require treatment with a statin, we will allow for this medication initiation, anticipating that the number of new statin starts will be balanced between the two groups due to randomization.

References:

## 7. RECRUITMENT

[figure not shown]
Rheumatology colleagues in the CUMC Division of rheumatology will be informed about the current study during regular divisional research meetings where ongoing research projects in the division is reviewed and also during day to day discussions among faculty and fellows.

150 adult patients with RA will be recruited from the patient population seen in the rheumatology private practices and clinics at New York Presbyterian Hospital and Columbia University Medical Center. A letter (attached to the protocol as Appendix XXIX) will be sent on behalf of the Columbia rheumatology physicians to all the patients with Rheumatoid Arthritis followed by the above rheumatologists inviting them to participate in the study. A follow-up phone call by the study coordinator may also take place within a week of mailing out the letters to answer any questions the patients may have.

Flyers (see Appendix XIX) will be available in the waiting area of the rheumatology clinics informing the patients about the ongoing study.

For the enrollment of the controls the following process will be followed: Every RA patient enrolled in the study will be asked whether they could notify and refer friends without RA who may be willing to participate in the study. Referred friends will be asked to communicate by telephone with our research coordinator in order to review eligibility and then arrange the first visit if eligible and willing to consent.

In addition flyers describing the study and tailored for recruitment of non-RA controls will be available in the waiting

rooms of the internal medicine clinics of the New York Presbyterian Hospital (see Appendix XX). Non-RA subjects who are interested in participating will use the contact information provided on the flyers to contact our research coordinator and undergo review of eligibility before proceeding to the consent process.

## 8. INFORMED CONSENT PROCESS

As noted above, patients will be informed of this study by their treating physician and, if the patient expresses an interest in participating, the Principal Investigator or Co-Investigator or the Study Coordinator will explain the study and review the IRB approved consent form in detail. Each potential subject will have the opportunity to ask questions. Each potential subject will reiterate in his or her own words the purpose of the study, the risks, the benefits, and the alternatives to participating. Individuals who decide to participate in the study will provide written consent. The investigator will also sign and date the consent form. One copy of the consent form will be given to the subject and the original will be filed in the study's research file. Those who want to sign the consent form immediately will be allowed to do so, but will be encouraged to take the consent form home and discuss the study with their family and/or significant other before deciding whether or not to participate.

Patients who are not fluent in English will be provided with an appropriate IRB approved translation of the IRB approved English consent form. The consent form discussion will take place with the assistance of a translator or bilingual member of the study team. Due to the demographics of our local population, we anticipate the need for a Spanish translation and will obtain a certified Spanish translation of the consent form as soon as the English version is approved by the IRB. We have accessibility to Spanish translators to assist with consent form discussions and other study visits and at least two member of our study team are bilingual. Translators are also available through the hospital should the need arise.

## 9. CONFIDENTIALITY OF STUDY DATA

All data and specimens collected during this study will be assigned a unique code number and will be separated from the patient's name and any other information that could identify the patient. The data file and the file that links the unique code number to patient identity will be maintained in separate password protected files on password protected computers in a locked office in the Division of Rheumatology. Only the Principal Investigator and key study personnel designated by the Principal Investigator will have access to these files. Those with access are held to the strictest standards of confidentiality. The results of this research may be published in scientific journals or presented at medical meetings, but patient identity will not be disclosed.

[figure not shown]
## 10. PRIVACY PROTECTIONS

The consent form discloses to potential participants the individuals and/or agencies that are able to look at and copy research records, namely:

- The investigator, study staff and other medical professionals who may be evaluating the study
- Authorities from Columbia University and New York Presbyterian Hospital, including the Institutional Review Board ('IRB')
- The Office of Human Research Protections ('OHRP')
- The Food and Drug Administration ('FDA')
- The sponsor of this study, the National Institutes of Health, including persons or organizations working with or owned by the sponsor

Information made available for inspection will be handled in strictest confidence and in accordance with local data protection laws.

In addition to confidentiality disclosures described in the consent form, potential participants will also sign the

attached study specific HIPAA Form before participating in this study.

## 11. POTENTIAL RISKS

A risk exists that despite all provisions to maintain participants confidentiality, confidentiality nonetheless may be compromised. As mentioned above every effort will be made to secure the data collected and separate identifying from deidentified information.

Phlebotomy is associated with minor discomfort and occasional patients may experience a more severe vaso-vagal reaction and light-headedness. A minor risk of a skin infection at the site of phlebotomy also exists but may be treated with a short course of antibiotics should it occur.

The mortality of the PET-CT imaging is low and associated mainly with the stress phase and administration of adenosine. In patients with established coronary artery disease, mortality is reported to be 2/10000 patients. The risk for an acute myocardial infarction is also reported to be 2/10000. These numbers will not be applicable to our participants as candidates with prior cardiovascular events will be screened out.

In addition the mortality at the Columbia university PET center has been 0% for PET-CT stress tests for the last 11 years with over 11000 PET-CT stress tests performed. Research participants with contraindications or risk factors for complications to PET-CT imaging and its stress phase (i.e., patients with cardiac blocks, or severe bronchospastic disease) will be excluded from the study.

The radiation exposure/dosimetry with PET-CT imaging is within FDA guidelines for research of this type. The radiation obtained during each PET examination in our protocol would be equivalent to few months of natural and cosmic radiation.

[figure not shown]
The additional 3 CT transverse images described above, the cardiac CT for CAC evaluation, and the DEXA are also associated with a small radiation exposure but no other significant risks. Female patients will be tested with a pregnancy test the morning of the day of each test associated with radiation exposure.

In addition the patients will have to be fasting overnight when they present for their study visits and this may cause mild discomfort.

In every study visit participants will be asked if they received radiation from imaging procedures outside the current protocol (for their clinical care). If other imaging studies have taken place the cumulative radiation exposure will be calculated and if it exceeds the level of 50 mSv which is considered to be the maximum acceptable radiation exposure per year then the subject will not continue with further participation in the study.

The testing performed in this study may unmask conditions that have been silent (asymptomatic). If a significant medical finding is noted during participation in this study, the P.I. will be notified immediately by study personnel, PET-CT or Echocardiography centers. Findings will be handled as "alerts", need for "urgent" or "immediate" referral. An "alert" refers to a medical finding that may have adverse health consequences if untreated. An "urgent referral" is made for abnormalities that require medical attention but not on an emergency basis. An "immediate referral" is a medical emergency that requires immediate notification of both the participant and his/her primary care physician. Examples of "immediate referrals" for PET-CT scans or echocardiography will include, pericardial effusions or pulmonary tumors.

If cause for an "immediate referral" is identified by clinical personnel or PET-CT or echocardiography personnel, the cardiologist or technicians will notify [name] immediately. [name] will then take appropriate medical action which will include informing the patient's primary care provider immediately. The less urgent "alerts" will be transmitted back to the PI from the Reading Centers within two weeks after receiving the scan. [name] will take appropriate action, which again will include notification of the patient's primary care physician. A record of all this

events will be maintained.

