After the escalation in their treatment at baseline (Study Visit I) these patients will return for a second (24 weeks) study visit respectively and the set of evaluations shown in the table below - and in more detail in Appendices I, II and III - will take place. A window of +/- 2 weeks will be allowed in scheduling the study visits.

Visit II	
Evaluations	Mar/2012-Jan/2015
Cardiac PET-CT scan*	X
3D Echocardiogram	X RA &
CV Questionnaires	X
Joint examination	X
DEXA scan (body composition)	X
Phlebotomy	X
Anthropometry	X

\*including 3 transverse CT slices (mid-chest, L4-L5, mid-thigh) and low dose radiation chest CT

During PET-CT scans a low dose CT imaging of the chest is always obtained for attenuation correction as part of the usual PET-CT protocol. Although we will not need a repeat coronary artery calcium score at visit 2, low dose radiation CT imaging of the chest is always obtained for attenuation correction as part of the usual PET protocol. During this CT imaging acquisition 3 additional slices (CT cuts) will be again obtained (mid chest, lumbar, and mid thigh) to evaluate for change in visceral fat following treatment initiation.

The 3-dimensional Echocardiogram (3D Echo) will be performed to provide a measure of LV mass and will be performed in every study visit.

The 15 controls will also be asked to have a repeat set of evaluations 6 months (24 +/- 2 weeks) after their first evaluation without any therapeutic or other intervention in between the two visits. The inclusion of non-RA controls will provide important data on the normal variation of cardiac PET-CT and 3D Echo parameters over time. Further evaluations for the control participant visits are outlined in appendices I, II and III.

Every subject (RA patient or non RA control) will have a urine pregnancy test prior to tests involving radiation exposure (PET-CT scan and DEXA) and on the same day.

The screening and consent process of a patient to receive randomized escalation of treatment will be made at the time they are consented for the first study visit. It is possible that all 150 patients will qualify for randomization of their treatment but only the first 50 of those will be selected to return for study visit II. The rest of the patients will exit the study and will continue their regular care with escalation of their treatment by their treating rheumatologist outside the study.

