Standard of care entails that patients who undergo escalation of their treatment need to be evaluated every 6-8 weeks to evaluate response to treatment, the need for further treatment escalation, and toxicity monitoring. Thus in between Study Visits I and II patients will return every 6-8 weeks for safety visits which will mirror standard of care management and which will be focused on toxicity monitoring as it would happen even if the patients did not participate in the study. An exit safety visit will occur 6-8 weeks after visit II. The incorporation of safety visits in the study and the related procedures/tests are shown in Appendices I and II.

It is possible that patients randomized to receive either the triple therapy or treatment with a TNF inhibitor and methotrexate may not respond to treatment. Disease activity will be evaluated using the Clinical Disease Activity Index (CDAI) score at the time of every safety and study visit and treatment will be modified until they reach the state of low disease activity or remission as defined by a CDAI score of less than or equal to 10. CDAI score takes into account the number of swollen and tender joints and the evaluation (using a Visual Analog Scale) of disease activity by both the patient and the physician. CDAI is an extensively validated disease activity tool.

[figure not shown]
The treatment algorithm followed in this study is described below. A study flow chart describing the algorithm is provided in appendix XXI.

i. Randomization to the non TNF inhibitor arm: Patients on triple therapy will be started on 1 gram of sulfasalazine (SSZ) twice daily along with weight adjusted daily Hydroxychloroquine (Plaquenil). Methotrexate treatment will be continued. It takes approximately 6 weeks before an effect of this therapeutic regimen is experienced. In the first safety visit (which will happen approximately 8 weeks after the first study visit) the need to increase the SSZ to 3 grams daily will be evaluated based on whether the patient has reached low disease activity status or remission. In the subsequent safety visit (safety Visit 2) which will occur 8 week after Safety Visit 1, if disease activity remains moderate or high, SSZ and Hydroxychloroquine will be stopped and patients will be switched to Leflunomide (Arava) 10 mg plus methotrexate.

Patients will then return at 24 weeks for their second Study Visit (Study Visit 2) for completion of the study and further management as per standard of care.

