As already mentioned, the goal of this study is to investigate the "low LV mass phenotype" in patients with RA and its contributors in an attempt to elucidate the pathophysiology pathways that may connect RA with alterations in the myocardium and the evolution to heart failure. 3D-Echo will be used to measure the LV mass. Cardiac PET-CT imaging will be used to evaluate myocardial function (cardiac output, ejection fraction), microvasculature function (myocardial perfusion) and myocardial inflammation (F18-FDG uptake).

The research questions to be addressed with the study visit I are the following:

- i) Are anti-CCP antibodies or other RA-specific characteristics (e.g., disease duration, activity, severity) associated with lower LV mass (or other LV parameters of structure/function)?
- ii) What is the prevalence, the degree and correlates of microvascular dysfunction in RA? Is it associated with low LV mass or reduced global or regional contractility? Is it associated with systemic, articular and/or myocardial inflammation?
- iii) What are the prevalence, patterns, distribution and severity of inflammation as measured by F18-FDG uptake in myocardial PET imaging? Are intensity and/or distribution of F18-FDG uptake correlated with low LV mass or global or regional contractility? Does the severity/distribution of F18-FDG uptake correlate with levels of systemic and/or articular inflammation?

For the second aim of this study the goal is to evaluate the effect of TNF inhibitors on the myocardium. For the 50 patients undergoing randomization and the controls the questions to be addressed will be the following:

- i) Are global measures of LV structure (e.g., mass) or contractility (e.g., ejection fraction) affected (reduced or increased) by treatment with TNF antagonists? Is there a different effect compared to alternative therapy?
- ii) If microvascular dysfunction and/or inflammation are present before treatment, do they improve with treatment with TNF compared to alternative treatment? If parameters improve only with TNF inhibitor, this would suggest that TNF inhibitors exert a local anti-inflammatory effect on the myocardium mechanistically different compared to alternative treatment.
- iii) If treatment-induced improvements in microvascular dysfunction and/or inflammation (F18-FDG uptake) are

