### Safety assessments

Toxicity monitoring, joint examination, general clinical examination vital signs (including blood pressure) will be assessed at every visit. In between Study Visits I and II patients will return every 6 to 8 weeks for safety visits per standard of care and which will be focused on toxicity monitoring. Interim safety visits will include the following laboratory assessments: CBC with differential, comprehensive metabolic panel, CRP, and ESR. An exit safety visit will take place approximately 8 weeks after the completion of study visit II and the evaluations mentioned above will take place as well. Study visits including radiation exposure (PET-CT, DEXA, x-rays) will include a urine pregnancy test for all female participants of childbearing potential. Disease activity will be evaluated using the CDAI score at the time of every safety and study visit and treatment will be escalated according to standard of care until they reach the state of low disease activity or remission as defined by a CDAI score of less than or equal to 10.

A copy of the Safety Visit Check Off Sheet is attached as Appendix XXVIII.

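### The 50 mSv rule ends all participation, so a randomised patient over the limit at Visit II also loses the radiation-free assessments, including the 3D-echo LV mass

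*Combined protocol and SAP*

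**What the plan says.** Section 11 (Potential Risks) sets the check: "In every study visit participants will be asked if they received radiation from imaging procedures outside the current protocol (for their clinical care"). Where there has been such imaging, cumulative exposure is calculated. The stated consequence is "then the subject will not continue with further participation in the study". The condition for applying it to the calculated total is "if it exceeds the level of 50 mSv which is considered to be the maximum acceptable radiation exposure per year". No exception is made for assessments without radiation, and no other section keeps such a participant in follow-up.

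The Safety assessments part of section 12 identifies the procedures that carry exposure: "Study visits including radiation exposure (PET-CT, DEXA, x-rays) will include a urine pregnancy test". Section 11 adds the three transverse CT images and the cardiac CT.

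On LV mass, section 2a states that "3D-Echo will be used to measure the LV mass", and that 3D echo "will be performed to provide a measure of LV mass and will be performed in every study visit". The Visit II table in section 2a also lists joint examination, phlebotomy, anthropometry and questionnaires. CDAI is scored at every safety and study visit. After that, "An exit safety visit will occur 6-8 weeks after visit II"; the treatment algorithm in the same section places this visit at 32 weeks.

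**The concern.** The rule is wider than the hazard it addresses. A limit on exposure calls for no more study radiation. It does not call for stopping an ultrasound examination, a joint count, a blood draw or a questionnaire.

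Whether LV mass changes under TNF inhibition, and differently from the alternative therapy, belongs to the first research question of aim 2. CRP and disease activity enter the fourth. Read literally, a patient who is over the limit at week 24 provides no Visit II value for any of these, although all could still be measured. The study's exit safety visit is lost as well.

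The trigger is imaging done for clinical care. In a randomised patient, imaging between the two visits comes after treatment has started, in an open-label comparison, and may reflect a medical work-up. Missingness that arises this way could be related to outcome. The statistical text in section 2a defines no analysis population and no handling of missing data for patients removed under the rule.

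**Working it through.** **1. What the rule removes, and whether it carries radiation**

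| Visit II item or later | Radiation? | Lost under the rule? |
|---|---|---|
| PET-CT with CT slices | yes | yes |
| DEXA | yes | yes |
| 3D echo (LV mass) | no | yes |
| Joint examination / CDAI | no | yes |
| Phlebotomy | no | yes |
| Anthropometry, questionnaires | no | yes |
| Exit safety visit, week 32 (clinical and laboratory) | no | yes |

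The first two rows follow from the purpose of the rule. The others do not.

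**2. When it acts**

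The question is asked at study visits. Patients who are not randomised have only Visit I, so they have no follow-up to lose. A randomised patient has two study visits, so the rule acts after randomisation mainly at Visit II. By then the interim safety visits have taken place.

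**3. The plan's own LV mass figure**

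Section 2b states more than 85% power for a 27 g difference between the arms. Inputs: SD 27 g (section 2b, RA patients), assumed equal at both visits; r = 0.35, carried over from the preceding within-arm sentence; 25 per arm; two-sided alpha 0.05 (section 2a).

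- SD of change = 27 × √(2 × (1 − 0.35)) = 27 × √1.3 = 30.8 g.
- Noncentrality = 27 / (30.8 × √(1/25 + 1/25)) = 3.10 on 48 degrees of freedom.
- Power = 86.0% by noncentral t (87.3% by normal approximation).

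The stated figure reproduces with these inputs and no dropout. With SDs of 27 g and 40 g at the two visits (SD of change 39.7 g), the same test gives 65.5%.

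**4. Effect of losing Visit II echoes**

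The same formula, counting only patients with both LV mass values:

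| Patients with both echoes | Power |
|---|---|
| 25 and 25 | 86.0% |
| 24 and 25 (one lost from one arm) | 85.2% |
| 22 and 25 (three lost from one arm) | 83.5% |
| 24 and 24 (one lost from each arm) | 84.5% |
| 21 and 21 (about the plan's 15% dropout: 25 × 0.85 = 21.25) | 79.2% |
| 20 and 20 (15% dropout plus one more from each arm) | 77.1% |

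One patient lost from one arm therefore costs about 0.8 points, and one lost from each arm about 1.5 to 2 points.

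**5. How many patients**

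The documents give neither mSv per study PET-CT nor a rate of outside imaging, so any count is an assumption. At assumed rates of 1%, 2%, 5% and 10% of the 50 randomised patients, the expected numbers are 0.5, 1, 2.5 and 5. Each patient is 1/25 = 4% of an arm.

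**The case against.** The strongest reply is that the rule will hardly ever be used. Section 11 likens each study PET to a few months of background radiation. Section 3 puts DEXA at 0.001 rem. Section 6 excludes people with prior cardiovascular events and, for the randomised part and the controls, those in other imaging studies. The randomised period is 24 weeks, and section 2b already allows 15% dropout. This stands as to size. A dropout allowance protects precision, however; it does not make an avoidable loss necessary.

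A second reply is that ending participation is coherent when the core imaging cannot be done. Aim 2 questions ii to iv all need PET perfusion or FDG data, cardiac output and ejection fraction come from PET-CT, and no primary outcome is named. This also stands in part: without a Visit II PET the patient informs only part of question i. It is no reason to discard that part. The mixed model can still use the Visit I value, but it cannot supply the missing change.

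Three stronger readings are tempting, and the documents do not support them.

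- A reader might infer that the loss is selective and biases the comparison of arms. The mechanism is plausible, but nothing in the documents says who receives clinical imaging, why, or whether it differs by arm.
- A reader might infer that safety follow-up as a whole is lost. For a randomised patient stopped at Visit II, what is lost is that visit's assessments and one exit visit. Safety visits mirror standard of care, so clinical monitoring can continue outside the study, although without study data.
- A reader might infer that everyone over the limit should stay in. That would keep, or even randomise, a patient already over it at Visit I with no baseline PET, which does not fit an imaging-based design.

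The order of procedures at Visit II is not given in the text available, so it cannot be said that every such patient would leave before the echo.

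**Conclusion.** The point holds as an inexpensive improvement to the wording, limited to participants who exceed the limit after their first visit. Section 11 stops radiation-free data collection that the exposure limit does not require stopping, and no other section restores it. For a randomised patient the avoidable loss is the Visit II echo LV mass, CDAI, blood draw, anthropometry, questionnaires and the week-32 exit visit.

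The effect is probably small: 4% of an arm per patient and, on the plan's inputs, about 0.8 points of LV mass power for one patient lost from one arm. Those power figures assume an SD of 27 g at both visits, r = 0.35 for the between-arm comparison, and analysis of complete pairs. Informative loss is possible, but its size and direction cannot be shown. The conclusion about the wording does not depend on any of these numbers, and the 50 mSv limit itself is not questioned.

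**What to change.** Leave the 50 mSv limit, and its effect on anyone over it before randomisation, unchanged. Add to section 11:

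> A randomised patient who exceeds the limit after Visit I will have no further study PET-CT, CT or DEXA, but will complete the non-radiation Visit II assessments (3D echo, joint examination/CDAI, phlebotomy, anthropometry, questionnaires) and the exit safety visit, and these data will be included in the analysis. A control who exceeds the limit after the first visit will complete the repeat 3D echo and the other non-radiation control assessments only.

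Controls need their own sentence because the documents describe neither a joint examination at the first visit nor safety visits for them.

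The cost is these two sentences and a matching line in the consent form, with no new procedure. The downside is that a few participants will have echo but no PET at Visit II. They will contribute to LV mass but not to the perfusion, FDG or PET-function outcomes, so the number analysed will differ between outcomes and should be reported for each.
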